9.5 Sample Size

This is a pilot, proof of concept study with the main goal of providing an estimate of the effect size difference between treatment and placebo control. As such the sample size of n=30 will provide sufficient estimates of the effect sizes necessary to power a future two-armed randomized study

9.6 Measures to Minimize Bias

9.6.1.1 Enrollment/Randomization/Masking Procedures

After receiving intranasal oxytocin for 9 weeks, participants will be randomized to either intranasal oxytocin or placebo. The fellow will use a random number generator to assign subjects to 0 (placebo) or 1 (active drug) each time a subject enters the randomized phase of the study. He will use block randomization so that treatment group assignments are balanced. This information will be created and stored in the Randomization Log. This will be kept securely, stored in a separate Randomization binder to ensure the non-blinded fellow only accesses the information as needed to randomize the study medication at visit 11.

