Reference Therapy	The investigational product will be compared to placebo, a nasal spray consisting of magnesium, chloride crystals, citric acid anhydrous gran., sodium citrate powder, sterile water for irrigation, and Pcca Mucolox liquid base.
Key Procedures	Oxytocin (or placebo) will be self – administered by the study participants daily. Study visits will occur every two weeks, from prior to the baseline week to 15 weeks after baseline, during which patients will be asked to rate the loudness of their tinnitus (VAS scale) and complete the THI questionnaire. Additional questionnaires and urinalysis will be performed at every study visit to monitor sodium levels and osmolality.
Statistical Analysis	The primary analysis is to provide an estimate of the partial eta squared effect size difference between placebo and treatment during the blinded phase of the study as well as to provide initial efficacy, safety and tolerability estimates during the initial open label study phase.

Schematic of Study Design

1 Key Roles

Primary investigator: [name] NYU Langone Medical Center [name] [name] [contact]

Sub-investigator (Headache Fellow): [name], MDNYU Langone Medical Center [name] [name] [contact]

Research Coordinator, Regulatory Specialist, Data Management, and Primary Contact: [name] NYU Langone Medical Center [name] [name] [contact]

2 Introduction, Background Information and Scientific Rationale

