- 3. A 6 week double-blinded phase in which half of the participants will receive oxytocin nasal spray and half will receive placebo nasal spray. Neither the PI nor subject will know which drug they are receiving. However, the study coordinator will have access to this information as required to assign the medications.

Patients will come to the Preston Robert Tisch Center for Men's Health for study visits every 2 weeks and be administered the VAS and THI/CGI scales by the research coordinator or principal investigator. The screening visit will be the most comprehensive and include obtaining informed consent, a physical exam with vital signs, laboratory studies, questionnaires, an ECG, and review of medical and medication history to confirm all inclusion criteria are met and that there are no exclusion criteria present. During these visits they will have urine testing for sodium and osmolality. Every other week, they will receive a phone call from study staff to discuss their experience using the study drug and monitor for any adverse effects. They will complete the Tinnitus Functional Index questionnaire over the phone as well. When the subjects come in for their study visit, 4 weeks after the baseline period, they will receive enough study medication for the rest of the study, to allow for randomization to placebo or active drug at that time.

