15.1 Study Leadership

The Study Team will govern the conduct of the study. The Study Team will be composed of the PI, Medical Fellow, and Research Coordinator.

16 Conflict of Interest Policy

The independence of this study from any actual or perceived influence, such as by the pharmaceutical industry, is critical. Therefore any actual conflict of interest of persons who have a role in the design, conduct, analysis, publication, or any aspect of this trial will be disclosed and managed. Furthermore, persons who have a perceived conflict of interest will be required to have such conflicts managed in a way that is appropriate to their participation in the trial. The study has established policies and procedures for all study group members to disclose all conflicts of interest and will establish a mechanism for the management of all reported dualities of interest.

Any investigator who has a conflict of interest with this study (patent ownership, royalties, or financial gain greater than the minimum allowable by their institution, etc.) must have the conflict reviewed by the NYU Langone Conflict of Interest Management Unit (CIMU) with a Committee-sanctioned conflict management plan that has been reviewed and approved by the study sponsor prior to participation in this study. All NYULMC investigators will follow the applicable conflict of interest policies.

17 References

- 1. Bhatt SM Bhatt JM, Lin HW, Bhattacharyya N. Prevalence, Severity, Exposures, and Treatment Patterns of Tinnitus in the United States. JAMA Otolaryngol Head Neck Surg. 2016 Oct 1;142(10):959-965.
- Moller AR. Sensorineural Tinnitus: Its Pathology and Probable Therapies. Int J Otolaryngol. 2016;2016:2830157. doi: 10.1155/2016/2830157. Epub 2016 Feb 8. Review. PubMed PMID: 26977153; PubMed Central PMCID: PMC4761664.

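### One unblinded sub-investigator generates, holds and applies the assignments after open-label response is known, so allocation concealment is not protected, and the block scheme is left unspecified

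*Combined protocol and SAP*

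**What the plan says.** Section 9.6.1.1 is the only place that describes how the sequence is generated.

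- **Method.** It says, of entry to the blinded phase: "The fellow will use a random number generator to assign subjects to 0 (placebo) or 1 (active drug) each time a subject enters". The next sentence adds: "He will use block randomization so that treatment group assignments are balanced". It does not give a block size, say whether blocks are fixed or varying, or say that a list is prepared in advance.
- **Storage.** "This information will be created and stored in the Randomization Log". The log sits in a separate, secure binder to "ensure the non-blinded fellow only accesses the information as needed to randomize the study medication at visit 11".
- **Who does it.** Section 1 lists the headache fellow as sub-investigator. Section 15.1 says: "The Study Team will be composed of the PI, Medical Fellow, and Research Coordinator".
- **Who else knows.** Section 4.1 says that "the study coordinator will have access to this information as required to assign the medications".
- **When.** Under Section 7.2.3.9 (Visit 11, Week 9), the VAS log is reviewed, THI and CGI-I are administered and adverse events are recorded. The participant is randomized at that same visit. Sections 4.1 and 7.1, however, place the supply that allows for randomization at a visit four weeks after the baseline period.
- **Target split.** Section 4.1 describes "A 6 week double-blinded phase in which half of the participants will receive oxytocin nasal spray and half will receive placebo nasal spray". Section 3 speaks of 15 participants in each group.
- **Replacement.** Section 5.7.2 replaces participants who leave early. It does not say how a replacement's arm is chosen.

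**The concern.** Allocation concealment requires that nobody who can influence whether, when or to what a participant is assigned can foresee or choose the assignment. Here one unblinded member of the study team does all three jobs: making the sequence, keeping it and applying it. The only safeguard described is a binder that this same person opens. The plan mentions no independent generator, sealed or central release, or pharmacy-held list.

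The timing sharpens the problem. In most trials little is known about a participant's response before assignment. Here everyone has been through the open-label phase, and VAS, THI, CGI-I and adverse events are reviewed at the randomization visit itself. If the next assignment can be foreseen or redrawn, it could be matched to a known responder or non-responder. Discretion over withdrawal before randomization (Section 5.7.1.1) would be another route. The primary outcome compares VAS areas between two arms of about 15, so a few steered assignments could shift the estimated effect size that the pilot exists to provide. Section 9.4.6 also relies on randomization to remove bias.

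The second, smaller question is whether the wording delivers the intended 1:1 split.

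**Working it through.** **Plan's own figure.** Section 4.1 allots half to each arm, and 30/2 = 15, which agrees with Section 3. Section 9.5 gives no alpha, power, effect size or standard deviation, so there is no sample-size calculation to reproduce.

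**Predictability under blocks.** The plan states no block size, so the sizes here are assumptions. Take a fixed, known block size b with h = b/2 per arm, and an observer who sees past assignments. An assignment is certain once one arm is used up within the block, which makes it part of the final run of identical assignments. The h assignments to one arm fall at random into h + 1 gaps around the other arm's h. The expected length of the final run is therefore 2h/(h + 1). The certain share is [2h/(h + 1)]/(2h) = 1/(h + 1).

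| Block size | Certain share | Best guess correct |
|---|---|---|
| 2 | 1/2 = 50% | 75% |
| 4 | 1/3 = 33% | 71% |
| 6 | 1/4 = 25% | 68% |
| 8 | 1/5 = 20% | 67% |
| 10 | 1/6 = 17% | 65% |

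The last column comes from exact enumeration, guessing the arm with more places left in the block.

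**Balance under blocks, 30 randomized, no dropout.**

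- Sizes 2, 6 and 10 divide 30, so the split is exactly 15:15.
- Size 4 leaves two places of an incomplete block. P(15:15) = (2 × 2)/C(4,2) = 4/6 = 0.667; otherwise 16:14.
- Size 8 leaves six places. P(15:15) = C(4,3) × C(4,3)/C(8,6) = 16/28 = 0.571; otherwise 16:14.

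**Balance if draws were unrestricted.** With Binomial(30, 0.5), P(15:15) = C(30,15)/2^30 = 0.144, P(18:12 or worse) = 0.362 and P(20:10 or worse) = 0.099.

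**What imbalance costs.** The standard error of the arm difference relative to 15:15 is √[(1/a + 1/(30 − a))/(2/15)].

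- At 18:12: √(0.1389/0.1333) = 1.021, a rise of 2.1%.
- At 20:10: √(0.1500/0.1333) = 1.061, a rise of 6.1%.

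**Effect of replacement.** The plan gives no post-randomization dropout rate, so 10% to 30% is assumed. Simulating 40,000 trials per setting, with blocks of 2, 4 or 6 and replacement until 30 are evaluable, gives P(15:15 evaluable) of 0.41 to 0.44 at 10% dropout, 0.31 to 0.32 at 20% and 0.26 at 30%.

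**The case against.** The best defence is that the two sentences on method need not conflict. They are adjacent, and the second can qualify the first: a random number generator can be used inside blocks, with a new block drawn when the last is full. The log and binder also fit a stored list. This defence stands. A reader might infer that the two rules cannot both be followed, or that the chance of 15:15 is only 14%. The documents do not support either inference, because the 14% applies only to unrestricted draws and Section 9.6.1.1 says that blocks are used.

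A reader might also infer that every comparison in Section 3 depends on 15 versus 15. It does not. The first primary comparison uses all 30 participants against baseline, and the first secondary endpoint looks only at those switched to placebo. The primary analysis in Section 9.4.2 uses arm means, standard deviations and an effect size, none of which needs equal arms.

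On concealment, the defence is that the PI takes consent (Section 12.3.1.2) and is blinded (Section 4.1), and that nothing says the fellow enrols or rates anyone. That is correct. The documents show an unprotected process; they do not show that any assignment was repeated or steered, and a log is required. But the absence of an enrolling role does not supply concealment when the same person generates and applies the sequence and the response is already on file.

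The coordinator's access to the codes is a related matter. Sections 4.1 and 7.1 let the research coordinator administer the outcome scales. That is mainly a problem of blinding during follow-up and should be kept separate from allocation.

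**Conclusion.** The concern holds for concealment. Generation, custody and use of the sequence rest with one unblinded sub-investigator, at a visit where open-label response is known, and no independent step is described. Under a fixed, known block size of 2 to 6, between one quarter and one half of assignments could be named in advance by someone who sees earlier ones. This rests on assumed block sizes. The documents give no basis for estimating the size of any resulting bias in the VAS comparison.

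The balance question is a matter of clarity. With blocks of 2 to 10 the randomized split is at worst 16:14. Even with unrestricted draws the standard error rises only about 2% at 18:12 and 6% at 20:10. Replacement of dropouts disturbs the evaluable split more than the choice among small block sizes does.

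This should be changed, but as the documents stand it does not invalidate the pilot.

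**What to change.** For all remaining assignments:

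- Replace the per-subject draw with a 1:1 permuted-block list with varying, undisclosed block sizes. Someone outside the Study Team should prepare it, such as an institutional statistician or the compounding pharmacy.
- Release one assignment at a time, only after the participant is confirmed at Visit 11. A pharmacy-held list would do. REDCap would also do if its randomization function is available; Section 13.1 describes REDCap only as a data-capture system.
- State that a replacement takes the next assignment on the list.
- Reconcile Sections 4.1 and 7.1 (supply for randomization four weeks after baseline) with Sections 7.2.3.9 and 9.6.1.1 (randomization at Visit 11).

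The protocol is already at version 1.7, so a list made before the first Visit 11 may no longer be possible. Assignments already made should stand, with a record of how they were generated.

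The cost is modest set-up work and a short task for an independent list holder, with no extra participants. Varying, undisclosed sizes deny an observer the known block size on which certainty depends, though some guessing remains possible. The change does not guarantee equal evaluable arms after dropout, and it does not settle the coordinator's access to the codes.

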2.4.1.2 Known Potential Benefits

Subjects may or may not directly benefit from being in the study. Close medical monitoring of their symptoms may be a potential benefit if subjects are seen infrequently otherwise. Furthermore, if the medication is effective for tinnitus, participants may indeed improve. However, the overall benefit of participating in this research is that it may help others with tinnitus in the future.

3 Objectives and Purpose

The purpose of this study is to evaluate the effects of high-dose intranasal oxytocin for treating tinnitus.

The primary outcome measurement will be a change in the VAS at 3 timepoints:

1. Comparative endpoint of VAS of all 30 subjects at 9th week of treatment with active drug vs baseline.

2. Comparative endpoint during the cross-over phase of VAS at the 17th visit (15th week of study) between the 15 subjects who received placebo vs the 9th week of the non-blinded phase for the same subjects (when they were on active drug). This endpoint compares the 15 patients that were switched from active to placebo and compares their response on placebo (from the double blind phase) with their response on active drug (from the non-blinded phase) and compares them to the 15 subjects that remained on active drug during the entire study.

3. A parallel group analysis where we compare both arms in the last week of the double-blind phase—so in essence we are comparing those 15 who were on active throughout the entire study to those that started on active and changed over to placebo.

Secondary endpoints of interest are also defined a-priori:

1. A change in the THI by at least one grade contrasting the 9th week (end of the single blinded phase) and the 15th week of the study (end of the double blinded phase) between the 15 subjects who were switched from active drug to placebo.

2. A change in the THI by at least one grade during the last 2 weeks of the double-blind stage (weeks 14 and 15 of the study contrasting those on active drug vs. placebo.

Exploratory endpoints of interest include:

Clinical Global Impression (CGI) measured following the same approach of the primary endpoints. Tinnitus Functional Index (TFI) measured following the same approach of the primary endpoints.

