6.1.7 Starting Dose and Dose Escalation Schedule

All subjects will begin at a dose of 30 IU 4 times daily for 2 weeks. If no response is reported (defined as a decrease in VAS of < 2), they will have the dose increase by 5 IU per spray every 2 weeks, until a maximum dose of 45 IU 4 times daily. If patients report improvement (defined as improvement in VAS >3) at any dose, they will remain at that dose through the end of the second phase. In the event that the patient experiences a moderate side effect, the dose will be decreased to the previous dose for the remainder of this phase.

Subjects will be informed that depending on their responses, their dose may stay the same, be increased or decreased. Accordingly, after Visit 3, active drug will be dispensed at office study visits every 2 weeks during the non-blinded phase.

The dose for the oxytocin nasal spray will be 30, 35, 40, or 45 IU per puff to be administered four times per day. This dosage was determined by treating 2 patients (as described above) with tinnitus in our clinical practice. Both patients were initially treated with 16 IU oxytocin nasal spray daily as detailed in the Azevedo et al study (5). Both patients noted slight improvement, and over the course of several months the dose was gradually increased while following their clinical course and vital signs and laboratory studies. Maximum benefit was noted at a dose of 45 IU QID.

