9.4 Description of Statistical Methods

Data from this pilot study will be summarized separately for the non-blinded study phase and by study arm for the blinded study phases. The area under the VAS curve after subtracting baseline value will be determined using the linear trapezoidal method. These areas will be determined for the efficacy population using the last observation carried forward (LOCF). The mean and standard deviation for the non-blinded phase will be determined and the effect size for the mean area from zero calculated. For the blinded phase week 3 (after a 2 week "washout") will serve as the baseline and the area under the VAS curve from baseline will be calculated using LOCF imputation for missing post baseline data. To avoid potential cross-over effects from the 9 week non-blinded phase when all subjects receive active drug, after randomization, subjects will receive either active drug or placebo. The first 2 weeks of this 6 week period will be a washout period from statistical analysis. While subjects will still receive study drug, data collection for that phase will not begin until week 3 of that 6 week period. The mean and standard deviation in area under the VAS curve from baseline for each study arm will be determined and the partial eta effect size for the mean difference between study arms calculated. This summary will be performed for the per protocol study population as well to investigate the relative influence of missing data on the effect size determination.

Frequencies and percentages for the secondary safety and tolerability endpoints will be determined using the ITT patient population for the non-blinded study phase and all randomized participants during the nonblinded study phase. The other secondary endpoint, incidence of the change in THI of 1 point or greater, will be summarized by study arm for those participants providing at least 1 post-week 3 baseline THI measurement.

The analyses will be refined and adjusted in anticipation of study termination and data lock.

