9.4.7.3 Additional Sub-Group Analyses

Not applicable

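### Open-label response to oxytocin enters neither the randomisation nor the blinded arm comparison, so chance imbalance goes uncontrolled and the pooled effect size is hard to carry forward

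*Combined protocol and SAP*

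**What the plan says.** Section 9.6.1.1 describes the randomisation: "After receiving intranasal oxytocin for 9 weeks, participants will be randomized to either intranasal oxytocin or placebo". It adds "He will use block randomization so that treatment group assignments are balanced", with no response criterion, stratification factor or block size. Section 4.1 gives the ratio: "half of the participants will receive oxytocin nasal spray and half will receive placebo nasal spray".

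Section 9.3 takes all randomised patients with at least one endpoint measurement into the blinded efficacy analysis. Section 9.4 summarises AUC by arm, with "the partial eta effect size for the mean difference between study arms calculated". Section 9.4.2 repeats this without a covariate. Section 9.4.6 relies on randomisation to remove bias.

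Open-label response is defined, but only for titration. The escalation rule in Section 6.1.7 (also in 4.1) begins "If no response is reported (defined as a decrease in VAS of < 2", and a separate clause defines improvement as a VAS gain above 3. Section 2.3 justifies the run-in as the way to learn the true response rate to active drug.

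Additional sub-group analyses (9.4.7.3) are "Not applicable". The nearest summary, by dose group in Section 9.4.7.6, covers the active arm only.

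**The concern.** Every participant enters the blinded phase after weeks on active drug, so the randomised contrast is continuing versus stopping. How large that contrast is may well depend on how many participants were benefiting when they were randomised. The plan collects this information and calls it the purpose of the run-in, then uses it in neither the allocation nor the primary comparison.

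Two things are at stake. With about 15 per arm, responders can fall unevenly between arms, and the plan neither prevents this nor adjusts for it. In addition, Sections 9.2 and 9.5 intend the effect size to power a later trial. A pooled figure from an unreported mix of responders and non-responders is hard to transfer to a population with a different mix.

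**Working it through.** **Inputs.** From the documents: 30 participants (Section 9.5) and 15 per arm (Section 3). Section 9.5 gives no alpha, power, SD or target precision, so n=30 cannot be reproduced. The documents also give no responder share, no size of loss on placebo and no VAS SD. These are assumed below, with ranges.

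**1. Chance imbalance.** With R responders among 30 and an unstratified 15:15 split, the number X on placebo is hypergeometric. For R=12, P(X=x) = C(12,x)·C(18,15−x)/C(30,15). In each direction:

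- 8:4 has probability 0.1016
- 9:3 has probability 0.0263
- 10:2 has probability 0.0036
- 11:1 has probability 0.0002

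The sum is 0.1317. Doubled, it is 0.263, or 26%.

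Other counts: R=18 gives the same 26%. R=15 gives 47% for 9:6 or worse and 14% for 10:5 or worse. For R=12, Var(X) = 15 × 0.4 × 0.6 × 15/29 = 1.862, so the SD of the between-arm difference in responder share is 2 × √1.862 / 15 = 0.18. It is 17 to 19 percentage points for R from 9 to 21. Blocks within response strata would hold the difference in responder count to at most 1 (blocks of 2) or 2 (blocks of 4).

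**2. Precision gained by adjustment.** Assume that responders on placebo lose L VAS points, everyone else changes by 0 on average, the SD is 1.5, and 12 of 30 are responders.

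- Unadjusted variance of the arm difference: 2 × 1.5²/15 + L² × 1.862/15² = 0.300 + 0.00828·L².
- Stratum-standardised variance (weights 0.4 and 0.6): the average over x of 0.16 × 2.25 × [1/x + 1/(12−x)] + 0.36 × 2.25 × [1/(15−x) + 1/(3+x)]. This is 0.312 (SE 0.559), whatever L is.

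| L | Unadjusted variance (SE) | Change in variance after adjustment |
|---|---|---|
| 1 | 0.308 (0.555) | no gain (about 1% worse) |
| 1.5 | 0.319 (0.564) | about 2% less |
| 3 | 0.375 (0.612) | about 17% less (16% from SEs rounded to 0.61 and 0.56) |

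Exactly balanced strata (6:6 and 9:9) would give 0.12 + 0.18 = 0.300. Stratified blocks therefore remove about a further 4% of the adjusted variance (0.312 to 0.300).

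**3. How the pooled effect size moves with the mix.** In the same model with responder share p, d = pL / √[(2.25 + 2.25 + p(1−p)L²)/2] and η² = d²/(d²+4).

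| L | Responders only | p=0.4 | p=0.6 |
|---|---|---|---|
| 3 | d=2.0, η²=0.50 | d=0.66, η²=0.10 | d=0.99, η²=0.20 |
| 1.5 | d=1.0, η²=0.20 | d=0.38, η²=0.03 | d=0.57, η²=0.07 |

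In each row the same responder effect gives pooled values of η² that differ about twofold with the mix. Parts 2 and 3 model a simple VAS change and are not on the scale of the planned AUC.

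**The case against.** A reader might infer that non-responders contribute nothing, so that a drug meeting the plan's success mark in responders (η²=0.5, d=2.0) is bound to look weak when everyone is pooled. The documents do not support that, for these reasons:

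- **Endpoint.** The primary measure is AUC above a baseline reset at blinded week 3. Any relapse in the first two blinded weeks is subtracted away. With the plasma half-life of 3 to 17 minutes cited in Section 2.1, early relapse is plausible, and responders on placebo could then also score near zero.
- **Mechanism.** Section 9.4.2 expects placebo to stay flat and active to trend, not placebo to lose benefit. Non-responders may still improve. On the dispensing schedule, someone escalated at every step reaches the top dose only at Visit 9, about two weeks before randomisation. A fall of 1.5 points also counts as no response, yet it can be lost.
- **Estimand.** Randomising all completers validly estimates the average effect in that population. Chance imbalance is random error, not bias. The remedy leaves the pooled estimate in place.
- **Other outputs.** The effect size is not the only efficacy result. The plan also reports open-label AUC, a per-protocol version, and THI, CGI and TFI by arm. Section 3 sets the switched participants against their own week 9 and "compares them to the 15 subjects that remained on active drug during the entire study".

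All of this stands, and it limits the size of the point. It does not remove the gap: subtracting week-3 VAS adjusts for level and not for responder status, and none of these outputs compares the arms by open-label response.

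**Conclusion.** The point holds as a modest, inexpensive improvement. Open-label response is collected and is the stated reason for the run-in, but it enters neither the allocation nor the arm comparison. The primary estimate is valid without it.

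The firmest figure is the imbalance, which needs only an assumed responder count: 26% for 8:4 or worse with 12 of 30. The precision gain is uncertain, from nothing to about 17% of variance for assumed losses of 1 to 3 points with SD 1.5. How far the AUC effect size varies with response is unknown, because the documents give no responder share or SD and the model in the check is not that endpoint. The case for acting is interpretability for the next trial and protection against an unlucky split, not a demonstrated loss of effect.

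**What to change.** - **Section 9.6.1.1.** For participants not yet randomised, use small blocks within two strata of open-label VAS change at Visit 11. Set an analysis-only cut-off that covers every value, for example a fall of less than 2 versus 2 or more from the baseline-week mean. Keep it separate from the dosing definitions. Those leave changes from 2 to 3 unclassified, and the passages in Sections 4.1 and 6.1.7 must be reconciled in their own right.
- **Section 9.4.2.** Keep all randomised participants as the primary set. Adjust the arm difference for open-label VAS change (or stratum) and for the pre-randomisation week-9 VAS. Show the unadjusted value beside it, because the denominator of partial eta squared changes once covariates enter.
- **Section 9.4.7.3.** Pre-specify a descriptive arm contrast by open-label response with its interval, labelled exploratory and imprecise (about 6 v 6 at 40% responders).
- **Participants already randomised.** Apply only the adjustment and the contrast, written before unblinding. Section 9.4 already foresees refinement of the analyses before data lock.

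**Cost.** Wording in three sections, with no new data, visits or patients. Totals may end one or two off 15:15, one or two degrees of freedom are lost, and the responder estimate will be imprecise. The change does not repair the separate problem that the week-3 baseline removes any relapse in the first two blinded weeks.
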